3.1.3 Double-blind induction period (Week 12 dose through Week 15 dose)

All subjects who complete the Double-blind Treatment Period will enter the Double-blind Induction Period.

During the Double-blind Induction Period, subjects randomized to placebo during the Double-blind Treatment Period will be switched over to treatment with secukinumab 300 mg. The Double-blind Induction Period is defined as the Week 12 dose through the Week 15 dose. **Subjects must administer the Week 12 dose no later than 7 days after the Week 12 FDG-PET/CT scan.**

- **Secukinumab:** Subjects who were randomized to the secukinumab treatment group at Visit 2/Baseline will continue to self-administer secukinumab 300 mg (two s.c. injections of the 150 mg dose) at Week 12. In order to maintain the blind, these subjects will undergo a sham induction with weekly placebo injections at Weeks 13, 14, and 15.
- **Placebo:** Subjects who were randomized to the placebo treatment group at Visit 2/Baseline will begin to self-administer secukinumab 300 mg (two s.c. injections of the secukinumab 150 mg dose) weekly for four weeks at Weeks 12, 13, 14, and 15.

Self-administration of the Week 12 dose will take place at the study site, while the doses at Weeks 13, 14, and 15 will be self-administered at home.

All subjects who discontinue study treatment prematurely for any reason before the end of Double-blind Induction Period should return to the study site for the performance of the Visit 14/Week 52 End of Treatment 2 (EOT2) assessments. The EOT2 visit should be scheduled 28 days (± 7 days) after the last dose of study treatment.

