The first study treatment self-administration will occur at Visit 2/Baseline after inclusion/exclusion criteria have been confirmed, all scheduled study assessments have been performed, and the clinical report from the Visit 2/Baseline FDG-PET/CT scan has been received and reviewed with no clinically important findings that would preclude the subject from continuing in the study. The first dose of study treatment will take place under the supervision of the Investigator/qualified site staff. The subject will be instructed on the use of the secukinumab/placebo prefilled syringe via review of the secukinumab IFU. At subsequent visits, the Investigator/qualified site staff will observe the self-administration of secukinumab/placebo at the site.

Administration

Each dose of study treatment (two prefilled syringes of secukinumab 150 mg or placebo) will be packed in an individual box. For further details about study treatment storage and handling, please refer to the secukinumab IFU distributed as training material for the study.

During the Double-blind Treatment Period (from Randomization through Week 8), subjects will self-inject a total of 12 secukinumab or placebo injections (two injections per visit).

During the Double-blind Induction Period (from Week 12 through Week 15), subjects will self-inject a total of 8 injections (two injections at Week 12, and two injections at home at Weeks 13, 14 and 15).

During the Open-label Treatment Period (from Week 16 through Week 52), subjects will self-inject a total of 18 injections (two injections per visit at Weeks 16, 24, 32, 40, and 48 and two injections at home at Weeks 20, 28, 36, and 44).

Date and time of secukinumab or placebo self-administrations during the study must be recorded on the Dosage Administration Record eCRF.

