#### **2.1.1.4 Day of last dose of randomized study treatment**

The date of last dose will be collected via the CRF.

Duration of exposure is defined in [Section 2.4.1](#).

If a subject discontinued early, then the last visit during the treatment period is considered (e.g., last visit in the induction period, if patient discontinued from the induction period) to calculate the duration of exposure.

On-treatment is defined as assessments within last dose plus 84 days.

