## **2.4 Treatments (study treatment, rescue medication, concomitant therapies, compliance)**

### **2.4.1 Study treatment exposure and compliance**

The duration of exposure to study treatments will be presented based on safety set.

Duration of exposure is defined as the time from first dose of study treatment to the time of treatment switch (for subjects who switch treatment) or end of treatment period. For subjects who discontinue duration of exposure will be the last visit in the corresponding treatment period. For example if a subject discontinues during induction period, this will be the discontinuation date from induction period recorded on the induction period completion CRF page.

Duration of exposure (days) = min (last study visit (including follow-up if applicable) date, last dose date +84) – first dose date +1

Duration of exposure (years) = duration of exposure (days) / 365.25

The duration in days will be summarized by treatment, descriptively and using frequencies and percentages for categories: “≥4 weeks”, “≥12 weeks”, “≥16 weeks”, and “≥52 weeks”.

More precisely, duration of exposure will be summarized for following categories:

“any exposure”, “≥1 week”, “≥2 weeks”, “≥3 weeks”, “≥4 weeks”, “≥8 weeks”, “≥12 weeks”, “≥16 weeks”, “≥28 weeks”, “≥40 weeks” and “≥52 weeks”.

Compliance as percentage of injections administered will be calculated as the number of injections applied (based on documented study drug administrations and syringe counts as given in the dosage administration record eCRF page) divided by the number of injections scheduled per protocol.

Compliance (%) = 100\*(total no of injections administered)/ (no. of injections prescribed).

Compliance to study treatment will be summarized descriptively and by categories:

<80% and 80% to 100%, by treatment.

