#### **2.8.1 Adverse events (AEs)**

All treatment emergent adverse events starting on or after the first dose of study treatment and until the last dose of study treatment plus 7 days (30 days for serious adverse events [SAEs]) will be included in all summaries and listings. Adverse events occurring after signing of informed consent but before first dose of study treatment and those occurring after 7 days of last study treatment (30 days for SAEs) will be listed only.

All adverse events will be coded using the MedDRA dictionary and summarized by system organ class and preferred term using frequency and percentage.

Primary system organ classes will be sorted alphabetically and, within each primary system organ class, the preferred terms will be sorted in descending order of frequency.

If a patient reported more than one adverse event with the same preferred term, the adverse event will be counted only once. If a patient reported more than one adverse event within the same primary system organ class, the patient will be counted only once at the system organ class level.

In addition following information will be listed by treatment group:

- Severity grade
- Relationship to the study treatment
- Duration
- Whether it constitutes a serious adverse event
- Action taken regarding study treatment
- Concomitant medication(s) taken or non-drug therapies given
- Outcome

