#### **2.8.2 Deaths**

Any death occurring between study day 1 and last day of treatment exposure + 30 days will be summarized by system organ class and preferred term for each treatment group and listed along with primary reason for death. Death occurring in the screening period and after 30 days of last dose of study treatment will be flagged.

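### The exposure formula in SAP 2.4.1 has no floor at the last dose, so it can end exposure 7 to 28 days before a recorded home dose that no visit follows

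*SAP*

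**What the plan says.** SAP 2.4.1 gives the formula as "Duration of exposure (days) = min (last study visit (including follow-up if applicable) date, last dose date +84", from which the first dose date is subtracted and one day added. The prose above it treats early leavers in two ways. It first says "For subjects who discontinue duration of exposure will be the last visit in the corresponding treatment period". Its example, for someone who stops during induction, is then a different kind of date: "this will be the discontinuation date from induction period recorded on the induction period completion CRF page". SAP 2.1.1.4 again points to the last visit in the period, and adds that "The date of last dose will be collected via the CRF".

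The protocol places seven doses away from the site. Section 3.1.3 has the Week 12 dose given at the site, "while the doses at Weeks 13, 14, and 15 will be self-administered at home". Section 5.5.4 lists, for the open-label period, "two injections at home at Weeks 20, 28, 36, and 44".

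SAP 2.8.2 uses two anchors for deaths. Its first sentence reads "Any death occurring between study day 1 and last day of treatment exposure + 30 days will be summarized". Its second flags deaths later than 30 days after the last dose. The SAE summaries in SAP 2.8.1 also count 30 days from the last dose.

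**The concern.** A minimum of last visit and last dose plus 84 days gives a sensible end date only if the last visit falls on or after the last dose. With home dosing that is not guaranteed. A subject who injects at home and is never seen again has a last visit that precedes the last dose. The formula then excludes from exposure the very interval in which a documented injection was given.

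Three things are at stake, all in the safety tables. Exposure is understated for people who leave without returning. The prose and the formula can lead two programmers to different end dates for the same subject. And if the end of exposure also sets the window for the death summary, that window could close too early.

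**Working it through.** The documents state no exposure figure to reproduce, so the check is date arithmetic.

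Inputs:
- Nominal study day = 7 × week + 1. This reproduces the scheduled days in SAP Table 1-1 (Week 12 = 85, Week 16 = 113, Week 24 = 169, Week 32 = 225, Week 40 = 281, Week 48 = 337, Week 52 = 365).
- Dose occasions (Protocol Table 5-1 and Section 5.5.4): 6 + 4 + 9 = 19, of which 3 + 4 = 7 are at home.
- The first dose is on Day 1, so exposure in days equals the day number of the end date.

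For a subject never seen after the home dose, the formula gives min(last visit, last dose + 84) = last visit:

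| Last dose (home) | Last visit | Exposure by formula | Day of last dose | Gap | Exposure with floor at last dose |
|---|---|---|---|---|---|
| Week 13 | Week 12 | 85 | 92 | 7 | 92 |
| Week 14 | Week 12 | 85 | 99 | 14 | 99 |
| Week 15 | Week 12 | 85 | 106 | 21 | 106 |
| Week 20 | Week 16 | 113 | 141 | 28 | 141 |
| Week 28 | Week 24 | 169 | 197 | 28 | 197 |
| Week 36 | Week 32 | 225 | 253 | 28 | 253 |
| Week 44 | Week 40 | 281 | 309 | 28 | 309 |

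If the preceding visit lies at the edge of its window (± 2 days at Week 12, ± 7 days in the open-label period) and the home dose is on its nominal day, the gap runs from 7 − 2 = 5 to 28 + 7 = 35 days.

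*Exposure categories in SAP 2.4.1.* The ≥28 weeks threshold is 28 × 7 = 196 days. The Week 28 case has 169 days by the formula (below) and 197 with the floor (above). On nominal days no other row changes category.

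*Subjects who return.* Protocol 3.1.3 and 3.1.4 schedule the EOT2 visit 28 ± 7 days after the last dose. The formula then ends 21 to 35 days after the last dose, and there is no gap.

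*Completers.* The last dose is on Day 337 and the last visit on Day 365; min(365, 337 + 84 = 421) = 365. There is no gap.

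*Deaths, if the last day of treatment exposure in SAP 2.8.2 is read as the SAP 2.4.1 end date.* Take an open-label visit on day v, the home dose on v + 28 and the next visit on v + 56. The summary window closes on v + 30. Flagging starts after (v + 28) + 30 = v + 58. A death from v + 31 to v + 55, which is 3 to 27 days after the dose, is neither summarized nor flagged.

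*Effect on total exposure (assumption).* If all 84 subjects had a full year, the total would be 84 × 365 = 30,660 days. One affected subject removes at most 28 nominal days (28 / 30,660 = 0.09%). Eight would remove 8 × 28 = 224 days (0.7%). Eight is only an illustration, close to the 0.10 loss rate applied to 84. That rate was set for sample size at Week 12, not for the home-dosing periods.

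**The case against.** The strongest objection is that the case may seldom arise. Under Protocol 6.3, home doses reach the eCRF from a self-administration log that the subject brings to the next visit. A subject who never returns will often have no home dose transcribed. The last dose on the CRF is then the site dose, and there is no gap. The telephone check at home dosing could supply the information, but Table 6-1 places it among items kept in source documentation, and nothing says that a call creates an eCRF dose record. This stands as a limit on frequency. It does not remove the case: Protocol 6.3 requires all administered doses to be on the eCRF, and Section 5.5.11 has sites contact subjects or family when someone stops attending.

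The second objection is that the SAP prose already covers discontinuation during induction, through the date on the completion CRF page. That date could close the gap. But the formula names a different date, and neither version requires the end date to be on or after the last dose.

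A reader might infer more than the documents support:
- *That adverse event rates would be biased.* They would not. SAP 2.8.1 plans frequencies and percentages of subjects; no exposure-adjusted rate is specified.
- *That a placebo subject lost after the Week 15 dose would show a single day of secukinumab.* The printed formula runs from the first dose date, so it yields 85 days against 106.
- *That deaths would go unreported over much of the open-label period.* The four 25-day intervals add up to 100 of the 253 days from Day 113 to Day 365, but that is not an expected loss. It needs a recorded home dose, no later visit, and one particular reading of a phrase that SAP 2.8.2 does not define. The next sentence there counts from the last dose, and a fatal event within 30 days of the last dose would still enter the SAE summaries.

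**Conclusion.** The formula is wrong in a narrow, reachable case. When the last recorded dose is a home dose and no visit of any kind follows, exposure ends 7 to 28 nominal days before that dose. The consequence is a small understatement for a few subjects, with one category change on nominal days (the Week 28 dose). The number affected cannot be derived from the documents, and the percentages above rest on assumed counts. The primary and secondary efficacy analyses do not use this variable.

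Two inconsistencies in wording are real in any case: the prose and formula in SAP 2.4.1 name different end dates, and SAP 2.8.2 uses two anchors. Whether a death could fall between those anchors depends on how the undefined end of treatment exposure is read. Severity: minor.

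**What to change.** In SAP 2.4.1, replace the formula with:

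Duration (days) = min(max(last study visit date, last dose date), last dose date + 84) − first dose date + 1.

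This changes nothing when the last visit is on or after the last dose. Make the prose in SAP 2.4.1 and SAP 2.1.1.4 name the same end date, and either drop the discontinuation-date example or state how that date relates to the last study visit.

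In SAP 2.8.2, use one anchor for both the summary and the flag, last dose date + 30 days, which matches the SAE window in SAP 2.8.1. A death 3 to 27 days after an open-label home dose is then summarized under any reading.

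The cost is a few lines of SAP wording and one programming change. The SAP already states that the last dose date is collected on the CRF, and visit dates are already used in the formula. No new data are needed.

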#### **2.4.1.1 Visit window**

Visit-windows will be used for the data that is summarized by visit; they are based on the

study evaluation schedule and comprise a set of days around the nominal visit day. For any assessment, there are the protocol defined scheduled visits around which visit windows were created to cover the complete range of days within the study. In the following tables, the days are counted since the first dose of study treatment (study days) for safety assessments, and the days are counted since the date of randomization for efficacy assessments. These visit windows apply to measurements taken at every visit. For assessments collected less often different visit windows will be applied as detailed below. When visit windows are used, all visits will be re-aligned, i.e., they will be mapped into one of the visit windows. E.g., if the Week 4 visit of a subject is delayed and occurs on Day 46 instead of on Day 29, say, it will be re-aligned to visit window Week 8. In the case of major deviations from the visit schedule, or due to unscheduled visits, several assessments of a subject may fall in a particular visit window (either scheduled or unscheduled). Statistical approaches to handle multiple assessments in a given visit window are specified below.

**Table 1-1 Assessment windows for PASI and IGA assessment:**

Analysis Visit	Week	Scheduled Day	Visit Window
Baseline	BSL	1	-28 day to Day 1
Week 4	4	29	Day 2-43
Week 8	8	57	Day 44-71
Week 12	12	85	Day 72-99
Week 16	16	113	Day 100-141
Week 24	24	169	Day 142-197
Week 32	32	225	Day 198-253
Week 40	40	281	Day 254-309
Week 48	48	337	Day 310-351
Week 52	52	365	Day >=352

**Table 1-2 Assessment windows for DLQI**

Analysis Visit	Week	Scheduled Day	Visit Window
Baseline	BSL	1	-28 day to Day 1
Week 12	12	85	Day 72-99
Week 24	24	169	Day 100-197
Week 32	32	225	Day 198-253
Week 40	40	281	Day 254-309
Week 48	48	337	Day 310-351
Week 52	52	365	Day >=352

Note: Range of visit windows are discussed and agreed with CTT.

The analysis visit will be used for listing of visit and period for safety data.

### **Multiple assessments within visit windows**

When there are *multiple assessments* in a particular visit window, the following rules are applied to select one value “representing” the subject in summary statistics in a visit window.

- For baseline assessment:

For efficacy analyses, baseline is the last assessment (including unscheduled visits) obtained before the randomization. All assessments obtained after randomization are considered as post-baseline unless otherwise specified.

For safety analyses, baseline is the last assessment (including unscheduled visits) obtained before the first dose of study treatment. All assessments obtained after the first dose of study drug are considered as post-baseline unless otherwise specified.

- For post-baseline visit windows the following applies (unless otherwise specified):
  - for *quantitative variables*, the *closest* to the actual visit is chosen (if two assessments have the same distance, then the earlier one will be chosen);
  - for *qualitative variables*, the *worst* record is selected. It is noted that in the analyses performed, *worst* case is always well defined (e.g., for urine protein values “+” and “++”, the worst case is defined as “++”),
- in case qualitative variables are based on quantitative variables, e.g. PASI 75 response, the visit will be assigned to the quantitative variable, and this visit will be used for the derived qualitative variable.

Note: Target to background ratio (TBR) and cardiometabolic biomarker (CMB) data will be analyzed as per CRF visit. In CMB data analysis, if the patient is discontinued then the discontinued study visit will be mapped for analysis to the next visit of the last available assessment before discontinuation with in the same treatment period.

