3.1.2 Double-blind treatment period (Randomization through Week 12 pre-dose)

The Double-blind Treatment Period is defined as Randomization through Week 12 (prior to the Week 12 dose).

At the start of the Double-blind Treatment Period, eligible subjects will be randomized via Interactive Response Technology (IRT) in a 1:1 ratio to one of two treatment groups (secukinumab 300 mg or placebo). **Subjects must be randomized and receive their first dose of study treatment no later than 7 days after the FDG-PET/CT scan.**

- **Secukinumab:** secukinumab 300 mg (two s.c. injections of the secukinumab 150 mg dose) once weekly for five weeks (at Randomization, Weeks 1, 2, 3, and 4) followed by a dose after four weeks at Week 8 (last dose during Double-blind Treatment Period).
- **Placebo:** placebo (two s.c. injections of 150 mg secukinumab placebo per dose) once per week for five weeks (at Randomization, Weeks 1, 2, 3 and 4) followed by a dose after four weeks at Week 8 (last dose during Double-blind Treatment Period).

During the Double-blind Treatment Period, all subjects will attend study visits at Randomization, Weeks 1, 2, 3, 4, 8, and 12, and all doses of study treatment will be **self-administered at the study site**.

Assessments for the primary efficacy variable will be performed at Week 12 for both treatment groups **prior to** subjects receiving their Week 12 dose.

All subjects who discontinue study treatment prematurely for any reason before the end of Double-blind Treatment Period should return to the study site for the performance of the Visit 8/Week 12 End of Treatment 1 (EOT1) assessments. The EOT1 visit should be scheduled 28 days (± 7 days) after the last dose of study treatment.

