If the date of a TB work up is less than 12 weeks from the projected randomization date, then it is not required that the TB work up be repeated. However, the subject must repeat the QuantiFERON test performed by the central laboratory.

Unscheduled visits

[figure not shown]
Subjects may be seen at any time for an unscheduled visit, e.g., if they experience deterioration of psoriasis or AEs that in the opinion of the Investigator/qualified site staff need intervention or repeat laboratory testing. The assessment(s) performed at an unscheduled visit must include at minimum: an assessment of concomitant medication and procedures/significant non-drug therapies, vital signs, and an AE/SAE assessment. Any additional assessments performed are at the Investigator/qualified site staff's discretion. During an unscheduled visit, study treatment will not be administered.

Table 6-1 Assessment schedule

Period	SCR	Double-blind Treatment Period							Double-blind Induction Period			Open-label Treatment Period								Unscheduled Visit ^D		
Visit	1	2	3	4	5	6	7	8 / EOT1 A,B				9	10		11		12		13		14 / EOT2 C	
Week	-4 to BL ^E	BL	1	2	3	4	8	12	13	14	15	16	20	24	28	32	36	40	44		48	52
Visit window (Days)			±2	±2	±2	±2	±2	±2				±7		±7		±7		±7			±7	±7
Assessment																						
Obtain informed consent	X																					
Demographics	X																					
Inclusion/exclusion criteria ^F	X	X																				
Smoking and alcohol history	X																					
Psoriasis history / Prior psoriasis therapy / Psoriatic arthritis history	X																					
Cardiovascular medical history	X																					
Cardiovascular disease family history	X																					
Medical history / Current medical conditions	X																					
Prior and concomitant medications / Surgical and medical procedures	X	X	X	X	X	X	X	X				X	X		X		X		X	X	X	
Physical examination ^F	X	X						X					X							X	X ^d	
Height	X																					

Period	SCR	Double-blind Treatment Period							Double-blind Induction Period			Open-label Treatment Period							Unscheduled Visit ^D			
		1	2	3	4	5	6	7	8 / EOT1 A,B				9	10		11		12			13	14 / EOT2 C
Week	-4 to BL ^E	BL	1	2	3	4	8	12	13	14	15	16	20	24	28	32	36	40	44	48	52	
Visit window (Days)			±2	±2	±2	±2	±2	±2				±7		±7		±7		±7		±7	±7	
Assessment																						
Weight	X	X				X	X	X				X		X		X		X		X	X	X ^d
Vital signs	X	X				X	X	X				X		X		X		X		X	X	X
Lab analysis: Safety panel (chemistry, hematology) ^G	X							X						X							X	X ^d

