**Table 2-4 Rules for selecting values for analysis**

Timing of measurement	Type of data	Rule
Baseline	All data	The last measurement prior to first dose – note this may include measurements taken on the day of randomization (e.g. lab).
Post-baseline safety	Summary visit information (e.g. lab, ECG, vital etc.)	
The (non-missing) measurement closest to the target day will be used.
 
In the event two measurements are taken equally apart (e.g. 1 day before target date and 1 day after) the first one will be used.
 
If two measurements are taken on the same day then select the first one (using the time).
 
If two measurements are taken on the same date/time then use the first visit number (assuming this is the planned visit).
 
If two measurements are taken on the same date/time/CRF visit then use the average of two assessments

Post-baseline efficacy	All data except DLQI, EQ-5D and health assessment, PGIC	
The measurement closest to the target day will be used. In the event two measurements are taken equally apart (e.g., 1 day before target date and 1 day after), the earlier one will be used.
 
If two measurement are taken on the same day then select the first one using eCRF visit number.

Post-baseline safety	Summary visit information (e.g. laboratory values, vital signs, etc.)	
The (non-missing) measurement closest to the target day will be used. In the event two measurements are taken equally apart (e.g., 1 day before target date and 1 day after), the earlier one will be used.
 
If two measurements are taken on the same day then select the first one (using the time).
 
If two measurements are taken on the same date/time then use the first eCRF visit number (assuming this is the planned visit). If two measurements are taken on the same date/time/eCRF visit number then take the average value of these two results.

Post-baseline safety	Notable abnormalities (e.g.	The most extreme measurement in the window

---

Timing of measurement	Type of data	Rule
and efficacy	vital signs, PGIC) and CTCAE grading for laboratory values	will be used. Note this means a subject can have a notably high and notably low measurement within a window

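### The SAP's Week 12 window for PASI and IGA runs past the placebo group's switch to secukinumab, and the SAP leaves open which record-selection rule governs IGA

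*SAP*

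**What the plan says.** **The window.** SAP 2.4.1.1 places each PASI and IGA rating into an analysis visit by study day, counted from randomization for efficacy. Table 1-1 gives Week 12 a scheduled day of 85 and a window of Day 72-99. No condition refers to the Week 12 dose.

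**The switch.** Protocol 3.1.2 ends the placebo-controlled phase before that dose: "The Double-blind Treatment Period is defined as Randomization through Week 12 (prior to the Week 12 dose"). Protocol 5.2 moves the whole placebo group to secukinumab from Week 12, and footnote A of Table 6-1 puts every Visit 8 assessment ahead of dosing.

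**Where the SAP does guard the boundary.** Biomarker records from discontinued subjects are mapped only inside the same treatment period (SAP 2.4.1.1 and Table 2-4). SAP 2.7.3 stops EOT1 values being carried forward past the switch, in the text on continuous variables. No matching limit exists for PASI or IGA.

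**Several records in one window.** SAP 2.4.1.1, Multiple assessments within visit windows, introduces its rules with "For post-baseline visit windows the following applies (unless otherwise specified"). Quantitative variables take the closest record. For qualitative variables "the *worst* record is selected". A further bullet covers the case "in case qualitative variables are based on quantitative variables, e.g. PASI 75 response", where the visit chosen for the quantitative variable is used. Table 2-4 has a row for post-baseline efficacy with the scope "All data except DLQI, EQ-5D and health assessment, PGIC" and the rule "The measurement closest to the target day will be used".

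**Extra ratings.** Protocol Section 6 allows unscheduled visits, for example "if they experience deterioration of psoriasis or AEs that in the opinion of the Investigator/qualified site staff need intervention". PASI and IGA at such visits are at the investigator's discretion (Table 6-1, footnote D).

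**The concern.** PASI 75/90/100 and IGA 0/1 at Week 12 are the skin endpoints compared with placebo. If a rating made after the Week 12 dose can stand for Week 12, a placebo subject's result may reflect active drug. The estimated difference and its confidence interval then no longer describe the comparison that the protocol defines.

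The second matter concerns IGA only. Protocol 3.6 describes it as a scale of five categories, so a programmer could class it as qualitative and take the worst record. Another could follow the efficacy row of Table 2-4 and take the closest. Because deterioration is a named reason for an unscheduled visit, the worst-record reading would favour flare visits for IGA while PASI came from the visit nearest Day 85. The two scores could then come from different days for the same subject.

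**Working it through.** 1. **Reproduce the window.** Scheduled day = 7 × 12 + 1 = 85. The limits are midpoints between neighbouring scheduled days: (57 + 85)/2 = 71 and (85 + 113)/2 = 99, so the window is Day 72-99, as in Table 1-1.

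2. **Overrun past the switch.** With the dose on nominal Day 85: 99 - 85 = 14 days. Visit 8 may fall on Day 83-87 (±2 days, Protocol Section 6), and the dose may follow the scan by up to 7 days (Protocol 3.1.2.1 and 3.1.3). The overrun therefore ranges from 99 - 83 = 16 days to 99 - (87 + 7) = 5 days.

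3. **Scheduled ratings after the dose.** Visit 9 falls on Day 113 ± 7 = Day 106-120. A discontinuation visit is 28 ± 7 days after the last dose (Protocol 3.1.3), so no earlier than Day 83 + 21 = 104. Both lie beyond Day 99. A post-switch rating in the window must come from an unscheduled or off-schedule visit.

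4. **When a post-switch rating wins under the closest rule** (dose on the day of the pre-dose rating; ties go to the earlier record):
   - Pre-dose rating on Day 83: distance 2, so Days 84-86 win. For example |86 - 85| = 1 < |83 - 85| = 2.
   - Day 84: distance 1, so only Day 85 wins.
   - Days 85-87: no later day wins.
   - Off schedule, Day 78: distance 7, so Days 79-91 win.
   - Visit 8 rating missing and no other pre-dose rating in the window: any post-switch rating up to Day 99 is used. Without such a rating, SAP 2.7.3 would count a placebo subject who stayed in the study as a non-responder.

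5. **Exposure at that rating.** With nominal doses on Days 85, 92 and 99, a placebo subject has had one secukinumab dose on Days 86-91 and two on Days 92-98; the third falls on Day 99.

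6. **Size.** One reclassified subject moves an arm by 1/42 = 2.4 points. The documents give no rate of unscheduled ratings, so an expected number cannot be derived. As a deliberately large illustration, assume 27/42 against 1/42 IGA responders, in line with Protocol Tables 3-1 and 3-2 (62-73% against 0-3%). The difference is 26/42 = 61.9 points, with Fisher p about 5 × 10⁻¹⁰. If five placebo subjects became responders, it would be 27/42 - 6/42 = 50.0 points, with p about 5 × 10⁻⁶.

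7. **The IGA rule under each reading.**
   - IGA as qualitative, general rule: worst record.
   - IGA 0/1 as derived from a numeric score: closest, by the bullet that names PASI 75.
   - Table 2-4 as the overriding specification: closest.
   - PASI responses: closest under both texts.

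**The case against.** A reader might infer that the SAP holds two opposite rules that cannot both be programmed. The text does not go that far. The general rules yield where something else is specified, and the efficacy row of Table 2-4 can be read as doing so, since IGA is not among its exceptions. IGA is also recorded as a 0-4 score, and response requires an improvement of at least 2 points (Protocol 6.4.4), which treats it as numeric. The only illustration of a worst record is urine protein, a safety test. What stands is an ambiguity: the SAP does not class IGA or say that Table 2-4 prevails. Table 2-4 also lists instruments that this trial does not schedule (EQ-5D, PGIC), so it is hard to rely on it as a deliberate override.

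A reader might also infer that because 14 of the window's 28 days follow the nominal switch, about half of the Week 12 data are exposed. The window's width does not measure exposure. Steps 3 and 4 show that an unscheduled or off-schedule rating is needed, and that an on-time pre-dose rating almost always prevails. The missing-rating route further requires that the Week 12 dose was given without assessments that the protocol places before it.

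The two problems should not be added together for IGA. If a pre-dose and a post-switch rating both lie in the window, the worst-record rule would discard an improvement after the switch; the Day 83/Day 86 example arises only under the closest rule.

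None of this supplies the missing limit on the window.

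**Conclusion.** The Week 12 window in Table 1-1 should be cut at the dose. Followed as written, it lets a rating made on secukinumab become a placebo subject's Week 12 PASI or IGA value, contrary to the protocol's pre-dose definition of the double-blind period. The IGA selection rule is unclear rather than contradictory, and that uncertainty does not reach PASI.

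The point is minor. It should affect few subjects, at about 2.4 points each with 42 per arm. It concerns secondary endpoints whose expected treatment difference is large, so the Week 12 conclusion would hardly change. TBR and the biomarkers are analysed by CRF visit and are not affected. This rests on visits being kept mostly within their protocol windows and on unscheduled ratings near Week 12 being uncommon. The documents give no figure for either.

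**What to change.** - **SAP Table 1-1:** for Week 12, accept only ratings taken before the subject's actual Week 12 dose, and count a Visit 8 rating on the dose date as pre-dose. Assign later ratings to the Week 16 window. They cannot displace an on-time Visit 9 under the closest rule, since Day 99 is 14 days from Day 113 and Visit 9 is at most 7.
- **Tie the cap to the dose, not to Day 85.** A subject who stops after the Week 8 dose (Day 57) has an EOT1 visit 28 ± 7 days later, on Day 78-92. That subject never switched and should keep the full Day 72-99 window.
- **SAP 2.4.1.1, Multiple assessments within visit windows:** state that IGA, like PASI, takes the record closest to the target day, as in Table 2-4.
- **SAP Table 1-2 (DLQI):** the same cap would do no harm, but no problem is shown there, because Table 6-1 marks no DLQI at unscheduled visits.

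The cost is two sentences in the SAP and a date comparison in the programming. No scheduled rating is lost. Both changes should be made before the Week 12 unblinding.
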